Individuals with depression or anxiety symptoms will be sampled in this study. Participants will be recruited from the placement organisations and promotions on social media, web pages, and at mental health centres. The sample size is estimated to be 300 individuals for initial screening for LIACT-guided self-help services.

Inclusion criteria

1. Adults aged 18-65
2. Adults with a specific set of presenting problems
3. Anxiety problems (including social, generalised, health anxiety, work anxiety)
4. Mild to moderate depression
5. Other emotional challenges include (but not limited to): Low self-esteem, perfectionism, mild anger issues, interpersonal or relational challenges, low motivation, lack of purpose, and numbness

Exclusion criteria

1. Adults with the following features/presentations are not eligible for the PWP programme and should automatically lead to an onward referral:
2. High severity on depressive score (PHQ9 \geq 20)

3. High or imminent risk (according to scores on PHQ9 question no. 9 and information emerging at triage assessment, including indication of plan and action or the lack of protective factor)
4. Any of the following presentations or situations: diagnosis or features of a mental health problem that is not suitable for low-intensity intervention, obsessive compulsive disorder, post-traumatic stress disorder, bipolar disorder, schizophrenia and other psychotic disorders, dissociative disorders, personality disorders, eating disorders, gender dysphoria, paraphilic disorders, anger issues as primary presenting concern (without anxiety or depression), sleep issues as primary presenting concern (without anxiety or depression), psychotic experiences (e.g. hallucinations), substance-related disorders, history of trauma or abuse that is considered highly relevant to the current presenting problem they are seeking support for, planned changes to psychotropic medication during the period of PWP intervention, currently receiving regular psychological counselling or support from another practitioner for at least twice a month, diagnosis of a learning disability, cognitive impairment or neurodevelopmental condition that would impair their ability to engage with a structured, manualised intervention (e.g. untreated ADHD or moderate-severe brain injury), clear safeguarding concerns requiring multi-agency support (e.g. concerns about domestic abuse)

Research design

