For training evaluation, given the current training programme has already consists of therapist competency assessment to ensure the quality of the training participants. A record of role-play videos will be rated the ACT therapist competency by trained psychologists at pre-training, after intensive training block, mid-placement and post-placement. A consent form will be sent to the training participant to authorise the use of data for analysis. Repeated measures design will be adopted for this study.

Repeated measures design will be adopted for this study. Individual guided self-help LIACT service, eligible participants will receive 6-8 sessions of guided self-help LIACT over three to four months. Clinical outcomes (depression and anxiety levels) will be measured at every session, it will take around 5 minutes to complete these two routine outcome measures. Other primary and secondary outcome measures, including general well-being, functioning and activity impairment, psychological flexibility, experiential avoidance, and therapeutic alliance will be at 3 time points, namely pre-treatment, post-treatment (at the end of the last session) and 6-week follow-up. Participants will take around 20 minutes to complete the full package of assessments. These outcome variables will be additionally measured after each

session to avoid missing data if participants drop out. Recovery rate and reliable improvement rate will also be used as indicators to evaluate the efficacy of LIACT. Focus groups will be conducted on participants who drop out and complete the programme to understand their experience and journey.

Curriculum

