1. General counselling skills - ENhancing Assessment of Common Therapeutic factors rating scales (ENACT; Kohrt et. al., 2015): The 18-item ENACT scale assesses the levels of common factors in psychotherapeutic settings. The domains covered include *non-verbal and verbal communication, rapport and self-disclosure, collaborative processes, problem-solving, assessing functional impairment* etc. Each item is rated on a scale from 1 (“needs improvement”) to 3 (“done well”).
2. ACT competency - The ACT Fidelity Measure (ACT-FM; O’Neill et. al., 2019): ACT-FM is a 25-item measure evaluating the clinicians’ fidelity to ACT according to four key aspects: *Therapist Stance, Open Response Style, Aware Response Style and Engaged Response Style*. The measure focuses on the therapists’ frequency of desired and unpreferred therapeutic behaviour. It is possible for therapists to demonstrate both ACT-consistent (e.g. “Therapist helps the client to notice thoughts as separate experiences from the events they describe”) and -inconsistent (e.g. “*Therapist imposes their own, other’s or society’s values upon the client*”) behaviours to co-exist, therefore, the scores are calculated into two separate subscales - ACT Consistency Score and ACT Inconsistency Score, both range from 0 to 36 marks.

Service evaluation.

1. Depression level: The PHQ-9 (Patient Health Questionnaire-9) is a widely-used self-report screening tool designed to assess the severity of depressive symptoms in individuals. The PHQ-9 contains nine items, each corresponding to one of the major depressive disorder criteria. Respondents are asked to rate the frequency with which they have experienced each symptom over the past two weeks on a 4-point Likert scale, ranging from 0 (not at all) to 3 (nearly every day). The total score ranges from 0 to 27, with higher scores indicating greater severity of depressive symptoms.

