2. Anxiety level: The GAD-7 (Generalised Anxiety Disorder-7) is a self-report questionnaire designed to assess the severity of generalised anxiety disorder symptoms in individuals. It comprises seven items, each reflecting a symptom of generalised anxiety disorder as outlined in the Diagnostic and Statistical Manual of Mental Disorders (DSM). Respondents are asked to rate the frequency with which they have experienced each symptom over the past two weeks on a 4-point Likert scale, ranging from 0 (not at all) to 3 (nearly every day). The total score ranges from 0 to 21, with higher scores indicating a greater severity of anxiety symptoms. The GAD-7 is widely used in clinical and research

settings for screening, diagnosis, and monitoring treatment outcomes in patients with anxiety disorders.

3. Well-being: The World Health Organisation - Five Well-Being Index (WHO-5) is a questionnaire that measures current mental well-being, originally developed to assess both positive and negative well-being. This five-question version uses only positively phrased questions to avoid symptom-related language. Response options are indicative of the frequency of particular feelings (e.g. "I woke up feeling fresh and rested.") in Likert format, ranging from 0 ("at no time") to 5 ("all of the time").
4. Functioning impairment: The Work and Social Adjustment Scale (WSAS; Mundt et. al., 2002) is a self-report measure developed to assess functional impairment in daily life across five domains: work, home management, social leisure, private leisure, and family relationships. Each domain is rated on a 9-point Likert scale, ranging from 0 (no impairment) to 8 (very severe impairment), with higher scores indicating greater functional impairment. The total score ranges from 0 to 40. The WSAS is commonly used to evaluate the impact of psychological disorders on an individual's daily functioning and to monitor treatment progress.
5. Psychological flexibility: The Acceptance and Action Questionnaire (AAQ-2; Bond et. al., 2011) is a widely-used measure designed to assess psychological inflexibility, which is a central concept in Acceptance and Commitment Therapy (ACT). In this 7-item self-report scale, participants choose from 1 ("never true") to 7 ("always true") to depict the relevance of the statements and themselves.

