6. Therapeutic alliance: The Working Alliance Inventory (WAI) was developed by Horvath and Greenberg in 1989. The brief revised version (Brief Revised Working Alliance Inventory; BR-WAI) consists of 12 items available multilingually (including Chinese). The scale is rated on a 5-point Likert scale, ranging from 1 (never) to 5 (always).
7. Experiential avoidance: The Brief Experiential Avoidance Questionnaire (BEAQ; Gámez et. al., 2014) is a shortened 15-item self-report measure designed to assess experiential avoidance, or the avoidance of uncomfortable or distressing thoughts and emotions. These statements are scored on a scale ranging from 1 (strongly agree) to 6 (strongly disagree).
8. Work Productivity and Activity Impairment: Work Productivity and Activity Impairment Questionnaire: General Health (WPAI) was developed by Reilly et. al. (1993) to measure impairments in both paid work and daily activities due to health-related problems. The domains covered include work time missed, impairment at work, productivity loss and activity impairment.

9.

Data analyses

For individual service, only the data of participants who have attended two or more follow-up sessions will be included for analysis. The first assessment session will not be counted for this requirement. Firstly, inter-correlations among all outcome measures will be assessed with Pearson's correlation coefficients. Secondly, the changes in outcome variables between pre-treatment, post-treatment and 3-month follow-up will be evaluated with repeated measures ANOVA. Cohen's *d* will be calculated to assess the relative effect sizes. Furthermore, reliable significant improvement will be computed according to the method recommended by Jacobson & Truax (1991), which is the division of pre-post treatment score difference by the standard error.

Compliance

The protocol of this study complies with the Declaration of Helsinki, IGH-GCP and research ethics principles to protect the rights, safety and well-being of participants.

References

doi:10.1111/j.1600-0047.2004.00329.x

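### Does the loose wording of the divisor in the reliable improvement index inflate the rate of reliable improvement?

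*Combined protocol and SAP*

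**What the plan says.** Under Data analyses, changes across the assessment points are evaluated with repeated measures ANOVA, and effect sizes are given as Cohen's d. The plan then adds an individual-level index: "reliable significant improvement will be computed according to the method recommended by Jacobson & Truax (1991", glossed as a calculation "which is the division of pre-post treatment score difference by the standard error". It states no cut-off, reliability coefficient, source for the SD or list of scales.

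The role of the index comes from Research design: "Recovery rate and reliable improvement rate will also be used as indicators to evaluate the efficacy of LIACT". Recovery is not defined anywhere.

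Two parts of the plan bear on who could count as recovered. The inclusion criteria go beyond anxiety and depression: "Other emotional challenges include (but not limited to): Low self-esteem, perfectionism, mild anger issues". They set no minimum PHQ-9 or GAD-7 score. The sections Mental Health in Hong Kong and Aims of the study, however, describe service recipients as people who screened positive for at least mild depressive or anxiety symptoms.

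**The concern.** A pre-post difference carries measurement error from two scores. Its error SD is therefore larger, by a factor of √2, than the standard error of measurement (SEM) of one score. A reader who takes the gloss alone, without the method named just before it, could divide by the SEM. The bar for reliable change would then be 29% too low (1 − 1/√2 = 0.29), and unchanged clients would be called improved too often.

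The service evaluation has no comparison group, so such misclassification would go straight into the reported percentage. The Introduction also cites a large service study with 40.3% reliable recovery and 63.7% reliable improvement, figures a reader may want to set beside this study's rates.

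The worry about recovery is similar. With no entry minimum, some clients may start below whatever cut-off is later used, and the rate then depends on how they are handled.

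**Working it through.** The plan states no error rate, threshold or cut-off for this index, so it has no figure of its own to reproduce. The check compares the possible readings of the divisor.

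**Inputs**
- From the plan: the numerator is the pre-post difference. The PHQ-9 runs from 0 to 27 and the GAD-7 from 0 to 21.
- Assumed: cut-off c = 1.96, with 1.645 and 2.576 as the range. Measurement errors are normal, independent and equal at both times, and there is no true change. SD and reliability r are needed only to express thresholds in points.

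**False improvement, one direction**
- Divisor is the standard error of the difference, SD × √2 × √(1 − r): rate = 1 − Φ(c).
- Divisor is the SEM, SD × √(1 − r): rate = 1 − Φ(c/√2).

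SD and r cancel in this comparison.

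| c | SE of the difference | SEM | Ratio |
|---|---|---|---|
| 1.645 | 5.0% | 12.2% | 2.4 |
| 1.96 | 2.5% | 8.3% | 3.3 |
| 2.576 | 0.5% | 3.4% | 6.9 |

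At 1.96 the effective value is 1.96/√2 = 1.386. Counting both directions, the rates are 5.0% and 16.6%.

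**In points**, with assumed SD 5 and r = 0.85: SEM = 5 × √0.15 = 1.94. The thresholds are 1.96 × 1.94 = 3.80 for the SEM and 1.96 × √2 × 1.94 = 5.37 for the SE of the difference. On an integer scale these mean drops of 4 and 6 points.

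**Which reading does the plan support?** The sentence places the calculation under a named method before paraphrasing it. The paraphrase divides a score difference by its standard error, and in ordinary usage that is the standard error of the quantity in the numerator. Nothing in the text mentions the error of a single score. A standard error of a group mean does not suit an index computed for each client. With n of 100 to 300 and r of 0.7 to 0.9 it would flag about 33% to 44% of unchanged clients, a result that would expose the mistake.

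**Recovery.** Suppose a fraction q of clients start below the cut-off and half of the true cases recover (both assumed).
- Counted as recovered: 0.5(1 − q) + q, which is 55% at q = 0.1 and 65% at q = 0.3.
- Kept in the denominator as not recovered: 0.5(1 − q), which is 45% and 35%.
- Restricted to cases: 50%.

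The first two options err in opposite directions, and the plan adopts neither. The figures show that a definition is absent, not that a stated rule is biased.

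**The case for a change.** The strongest case for a change is that the citation does not close every gap. The authors chose to spell out the calculation and left out the words that identify the divisor, and the misreadings examined all lower the bar. Even with the right divisor, the analyst must still choose the reliability, the SD and the cut-off, possibly after seeing the data. Those choices matter: at 1.96, with SD from 4 to 6 and r from 0.80 to 0.90, the correct threshold itself runs from 3.5 points (1.96 × √2 × 4 × √0.10) to 7.4 points (1.96 × √2 × 6 × √0.20). Recovery is open in the same way.

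The point about unstated inputs stands as an observation on completeness. It does not show that the plan prescribes an invalid index. Inflation requires the analyst to depart from the method the plan names, and the threefold figure also needs a 1.96 cut-off that the plan does not give. The comparison with the cited service figures carries less weight still, because the Introduction offers them as background and the plan commits to no such benchmark.

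**Conclusion.** The concern does not call for a change. The wording is a loose paraphrase of a named method, and an analyst who follows that method divides by the standard error of the difference. False reliable improvement is then 2.5% at an assumed 1.96 cut-off, with no inflation. The rise to 8.3% is correct arithmetic for a mistake the plan does not make. It rests on an SEM divisor, a 1.96 cut-off, normal independent errors and no true change, and whole-number scoring would shift the exact rates somewhat.

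What remains is missing detail of the kind analysts fill sensibly: the reliability, the SD, the cut-off, the scales, and who enters the recovery denominator. The two rates stand alongside the ANOVA and effect sizes, not in place of them. All the inputs can be reported with the results, so a reader can check the index or recompute it.
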